8.3 SAMPLE SIZE JUSTIFICATION

The anticipated sample size is approximately 3600 participants (CYP- parent/caregiver dyads). This sample size is based on the expected clinic prevalence of gender related distress (assuming 80% recruitment of those presenting at the CYPGS), allowing for sufficient power to detect meaningful differences and associations in the primary and secondary outcomes.

This sample size will allow for meaningful effect sizes to be determined within subgroups of this larger population. As an example, it is estimated that those diagnosed with neurodevelopmental traits or disorders will make up around 15% (540) participants in the Horizon cohort. With around a 50/50 split of birth registered males and females within this subgroup, sample size simulations estimate that it would be possible to determine a standardised effect size of approximately 0.32,

with an estimated 90% power between birth registered sexes within the Neurodivergent population.

8.4 STATISTICAL METHODS FOR PRIMARY AND SECONDARY OUTCOMES

Descriptive statistics will be presented for all outcomes, in the form of means and standard deviations for continuous outcomes, and count and proportion for binary or categorical outcomes. Tests will be carried out between the outcomes and the demographics to determine associations. Differences between the participant and parent reported outcomes, where both are available, will also be investigated. This will be done using paired t-tests or Wilcoxon signed-rank tests. Intraclass Correlation Coefficients will be calculated to assess agreement between the participant and parent reports.

Further information on analysis methods can be found in the Statistical Analysis Plan for PATHWAYS Horizon.

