2.1.2 Secondary Objectives

- 1. To improve understanding of how care options are experienced by CYP and their parents/carers/legal guardians.
- 2. To develop a novel interview-based outcome measure that focuses on CYP's aspirations and goals from gender care.
- 3. To explore similarities and differences in the holistic perspectives of CYP and their parents/carers/legal guardians to gain a comprehensive understanding of how gender incongruence affects CYP.

3. Participants & Recruitment.

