4.4.2.12 Difficulties in Emotion Regulation Scale (DERS)

CYP will complete the short version of the Difficulties in Emotion Regulation Scale (DERS-18), which consists of 18 self-report items measuring emotional difficulties ²⁷. The DERS-18 generates scores across six subscales: nonacceptance of one's emotions, lack of goal-directed behaviour

during negative emotions, impulse control during negative emotions, emotional awareness, access to emotion regulation strategies and emotional clarity ²⁸. The 29-item DERS-P²⁹ will be administered to parents/caregivers. The DERS-P generates scores across four subscales: catastrophise, negative secondary, attuned and distracted. Each item is scored using a 5-point Likert scale (1= almost never; 5= almost always) such that higher scores indicate greater difficulties in emotion regulation. The parent measure has been adapted to include gender neutral language. Duration: 4 minutes.

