4.4.2.15 Parental Attitudes of Gender Expansiveness Scale for Youth (PAGES)

The PAGES-Y³² is a 14-item self-report measure used to assess CYP's experience of parental acceptance of gender identity/ expression. The measure includes two subscales, perceived parental non-affirmation and perceived parental acceptance. CYP will rate each item based on their overall experience of support from both parents/caregivers within a single measure, as opposed to providing individual scores for each parent/caregiver. The PAGES-P³³ is a 16-item parent-report version measuring parental acceptance and support. Each item is responded to using a 5-point Likert scale (1= strongly disagree; 5= strongly agree), with higher overall scores indicative of greater perceived parental support. Duration: 3 minutes.

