8. STATISTICAL METHODS

8.1 **PRIMARY OUTCOME**

The primary outcome for the PATHWAYS-HORIZON study is the mental health status and wellbeing of children referred to national gender services for young people in the UK. This will be measured using the CYP self-report version of the KIDSCREEN-10 ²³ questionnaire, which evaluates quality of life across ten dimensions.

8.2 **SECONDARY OUTCOMES**

Secondary outcomes can be split into smaller subcategories. All outcomes are marked as to whether they are continuous, binary, time-to-event or will only be displayed descriptively. Scales of gender-related distress, mental health symptoms and physical health measures:

- Utrecht Gender Dysphoria Scale Gender Spectrum (UGDS-GS), continuous
- Revised Children's Anxiety and Depression Scale (RCADS), continuous
- Body Image Scale Gender Spectrum (BIS-GS), continuous
- Parental Attitudes of Gender Expansiveness Scale for Youth (PAGES), continuous
- SCOFF questionnaire, binary
- Sexual attraction questionnaire, descriptive only
- Adolescent Primary Care Traumatic Stress Screen (APCTSS), continuous
- Romantic Relations questionnaire, descriptive only
- Gender identity question, descriptive only
- Height (cm) and weight (kg) as BMI, descriptive only
- Physical health diagnoses, descriptive only
- Parental 'about yourself' questionnaire, descriptive only

Scales of suicidal ideation, hospitalizations, mood symptoms, behavioural and functional difficulties, quality of life ratings

- Ask Suicide-screening Questions (ASQ) for suicidal ideation and behaviour, binary
- Child Behaviour Checklist (CBCL), continuous
- Youth Self-Report (YSR) for behavioural and emotional problems, continuous
- KIDSCREEN-52 for quality of life, all 10 domains continuous
- Difficulties in Emotion Regulation Scale 18 (DERS-18), for young people, DERS-29 for parents, continuous
- Hospitalisations of participants, binary
- Social transition questionnaire, descriptive only

Experiences of therapeutic options

- Rates of referral to, uptake of and completion of:
- Psychological therapy, binary
- Occupational therapy, binary
- Speech and language therapy, binary
- Clinical nursing, binary
- Youth work support, binary
- School/College support, binary
- Non-endocrine pharmacological treatments, binary

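### Section 8.4 applies paired difference tests and ICCs to every dual-reported outcome, but the DERS forms, and to a lesser degree the PAGES forms, are not parallel

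*Protocol*

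**What the plan says.** Protocol section 8.4 sets one rule for comparing informants: "Differences between the participant and parent reported outcomes, where both are available, will also be investigated". On the test it says: "This will be done using paired t-tests or Wilcoxon signed-rank tests". On agreement it says: "Intraclass Correlation Coefficients will be calculated to assess agreement between the participant and parent reports". No instrument is excepted and no common metric is named. The section closes by referring to the statistical analysis plan for further information.

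The rule serves the third secondary objective in section 2.1.2: "To explore similarities and differences in the holistic perspectives of CYP and their parents/carers/legal guardians".

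The measures are described in section 4.4.2:

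- **DERS (4.4.2.12).** Young people complete the DERS-18, "which consists of 18 self-report items measuring emotional difficulties", scored on six subscales. Parents complete the 29-item DERS-P. "The DERS-P generates scores across four subscales: catastrophise, negative secondary, attuned and distracted". Items on both forms are scored 1 to 5. Section 8.2 lists the two forms on one line as a continuous outcome.
- **PAGES (4.4.2.15).** PAGES-Y has 14 items, and the young person rates both parents together. PAGES-P "is a 16-item parent-report version measuring parental acceptance and support". Items on both forms are scored 1 to 5.
- **APCTSS, ASQ and SCOFF (4.4.2.5, 4.4.2.10, 4.4.2.11).** Each parent form is described as built for direct comparison with the self-report. Nothing similar is said of DERS or PAGES.

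**The concern.** A paired difference test or an agreement ICC needs both informants to answer the same questions on the same scale. The protocol's own descriptions show that DERS does not meet this condition and that PAGES meets it only in part. Section 8.4 nevertheless covers both, because both reports are collected.

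Applied literally, the rule could yield a large and highly significant parent-child difference, and a poor ICC, that come from the questionnaires and not from the families. Because the objective is to describe where the two perspectives agree and differ, such a result could be published as disagreement about a young person's emotion regulation or parental support.

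**Working it through.** The protocol states no figure for this comparison, so there is none to reproduce.

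**Inputs from the protocol.** DERS: 18 and 29 items. PAGES: 14 and 16 items. All items are scored 1 to 5.

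**Assumptions, not in the protocol.** Scores are sums of items. Both informants have the same mean item response m (2.5 to 3.5) and the same SD s of the item mean (0.5 to 0.9). The correlation r is 1.0 or 0.6.

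**Step 1: range and built-in gap.** With a items on the young person's form and b on the parent's, totals run from a to 5a and from b to 5b. At equal mean response the gap is (b − a) × m.

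| | Young person's range | Parent's range | Gap at m = 2.5 | m = 3.0 | m = 3.5 |
|---|---|---|---|---|---|
| DERS | 18–90 | 29–145 | 11 × 2.5 = 27.5 | 33 | 38.5 |
| PAGES | 14–70 | 16–80 | 2 × 2.5 = 5 | 6 | 7 |

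**Step 2: effect on a paired test.** The SD of the difference is s × √(a² + b² − 2rab).

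- DERS with s = 0.8, r = 0.6, m = 2.5: 0.8 × √(324 + 841 − 626.4) = 18.6. The standardised gap is 27.5/18.6 = 1.48, and t with 1,000 pairs is 46.8.
- PAGES with s = 0.8, r = 0.6, m = 3.5: 0.8 × √(196 + 256 − 268.8) = 10.8. The standardised gap is 7/10.8 = 0.65.
- Over the full range of m and s at r = 0.6, t with only 100 pairs runs from about 13 to 33 for DERS and from about 4 to 10 for PAGES, with no true difference in item response.

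**Step 3: effect on the ICC.** In large samples the absolute-agreement ICC is 2·cov/(var₁ + var₂ + gap²), and the consistency ICC omits gap². Here cov = r·a·b·s², var₁ = a²s² and var₂ = b²s².

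- DERS with r = 1, s = 0.8, m = 2.5: 668.2/(745.6 + 756.3) = 0.445 for absolute agreement; 668.2/745.6 = 0.90 for consistency.
- DERS over the full range: 0.15 to 0.50 for absolute agreement at r = 1, and 0.09 to 0.30 at r = 0.6. Consistency is 0.90 and 0.54.
- PAGES over the full range: 0.69 to 0.93 for absolute agreement at r = 1, and 0.41 to 0.56 at r = 0.6.

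**Step 4: item means in place of sums.** Under the same assumptions the expected difference is 0 and the ICC equals r on both instruments. The content still differs: six subscales against four others for DERS, and two parents rated together against one parent's own report for PAGES.

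**Step 5: binary outcomes.** Section 8.2 also marks two dual-reported screens, ASQ and SCOFF, as binary ("SCOFF questionnaire, binary"). Paired 0/1 data were simulated with an assumed 35% endorsement by young people, and parent endorsement of 65% where the young person endorsed and 12% where not. The Wilcoxon test used the normal approximation and McNemar's test was uncorrected.

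| Pairs | McNemar p | Wilcoxon p | Paired t p | Kappa | ICC (absolute) |
|---|---|---|---|---|---|
| 100 | 0.394 | 0.394 | 0.396 | 0.503 | 0.506 |
| 500 | 0.1202 | 0.1202 | 0.1203 | 0.510 | 0.511 |
| 3,000 | 5.6 × 10⁻⁷ | 5.6 × 10⁻⁷ | 5.3 × 10⁻⁷ | 0.539 | 0.539 |

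**The case against.** The strongest reply is that section 8.4 is a general paragraph that points to the analysis plan. Scoring, the form of the ICC and the choice of comparable scale pairs are routine content there. The protocol never says that DERS-18 and DERS-P totals will be subtracted; section 4.4.2.12 speaks only of subscale scores. If item means or a consistency ICC were used, the most striking figures would shrink or vanish. For PAGES, section 8.2 names only the Youth form, so it is uncertain whether the parent form counts as an outcome under the rule.

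Much of this stands as a limit on size. The gaps in points depend on sum scoring and the low ICCs on the absolute-agreement form, and the protocol fixes neither. PAGES is the smaller and less certain case. The reply does not remove the defect, because 8.4 states a method with unrestricted scope and no choice of scoring makes forms with different content parallel. If the analysis plan already limits the instruments, 8.4 should say the same.

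A reader might also infer that ASQ and SCOFF would be given the wrong test. The documents do not support that. On paired 0/1 data the Wilcoxon test reproduces uncorrected McNemar, and the ICC is within 0.003 of kappa. Both screens also have totals (0–4 and 0–5) on forms designed to be comparable. Naming McNemar and kappa would be clearer but would change no conclusion.

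**Conclusion.** The point holds for DERS and, to a lesser degree, for PAGES. Section 8.4 prescribes paired tests and ICCs for pairs of forms that the protocol itself describes as different in length and content, so the results for those pairs could not be interpreted as parent-child difference or agreement.

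Under sum scoring and equal mean item responses of 2.5 to 3.5, length alone contributes 27.5 to 38.5 points for DERS and 5 to 7 for PAGES. It also lowers the absolute-agreement ICC for DERS to about 0.15 to 0.50 under perfect agreement. Under item-mean scoring the length effect is nil and only the content mismatch remains. A reader might conclude that the results are bound to reflect form length; that is conditional on scoring the protocol leaves open.

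Severity is minor to moderate. The objective is exploratory, and neither the primary outcome analysis nor the sample size depends on it.

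**What to change.** Amend section 8.4, and match the analysis plan to it, along these lines: *Paired difference tests and ICCs will be limited to instruments with parallel self-report and parent forms (for example KIDSCREEN, RCADS-25, APCTSS, ASQ and SCOFF, and CBCL/YSR on normed scores). For DERS and PAGES, the association between the two reports will be given as a correlation, or the reports will be compared on a common metric with its justification; no raw difference test or agreement ICC will be reported.* Section 8.2 should also make clear whether PAGES-P is an outcome.

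The cost is wording only, with no change to data collection. The raw DERS and PAGES difference tests are lost, but they were not interpretable.

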8.4.1 STATISTICAL METHODS FOR PRIMARY OUTCOME

The primary outcome will be analysed using a linear mixed model. This will account for the repeated measured design, and using maximum likelihood estimation allows for handling of missing follow-up data.

The fixed effects in the model will be timepoint, gender incongruence, age, site, neurodevelopmental conditions. The random effects in the model will be participant, to allow for random intercepts.

Estimates presented from this model will be point estimates and the 95% confidence intervals of those estimates.

8.4.2 STATISTICAL METHODS FOR SECONDARY OUTCOMES

8.4.2.1 Continuous outcomes

For continuous outcomes, the same analysis method will be used as are in the primary analysis. The fixed and random effects will also be the same as used in the primary analysis.

8.4.2.2 BINARY OUTCOMES

For binary outcomes, a similar method as used in the primary outcome analysis will be used. A mixed-effects logistic regression will be used in place of the mixed linear model.

The fixed effects and random effects will be the same as those used in the primary analysis.

8.4.2.3 TIME-TO-EVENT OUTCOMES

For time to event outcomes, a cox proportional hazards model will be used. Other models will be considered if the proportional hazards assumption does not hold.

8.5 INTERIM ANALYSES (STATISTICAL)

There is no planned interim analysis.

8.6 METHODS FOR ADDITIONAL ANALYSES (E.G. SUBGROUP ANALYSES)

The below CYP subgroups are planned to be used as subgroup analyses.

- Birth-registered sex
- Age at referral
- Neurodevelopmental and mental health diagnoses
- Social transition status
- Adverse life experiences

These analyses will be carried out using interaction terms in mixed models, and stratified analyses to compare separate analyses within each subgroup. Further subgroup analyses and analysis specifications will be detailed in the statistical analysis plan.

8.7 ANALYSIS OF NOVEL OUTCOME MEASURE

The primary aim is to establish the psychometric properties of the novel measure. The most important characteristics are inter-rater and test-retest reliability, but we also want to understand its convergent validity with the primary outcome measure, KIDSCREEN-10 and other outcome measures of mental health and behaviour, gender identity and body dysphoria. All of these established measures generate continuous scores.

Individual items in the novel measure will a priori map to measure domains, e.g., gender identity, emotions, family life, etc. Each domain will generate an individual score which will form a component of the total score. Domain will be ordinally or continuously distributed, and the total score will be continuous.

Inter-rater and test-retest reliability using intre-clss correlations (ICCs) will focus on the total score; while these characteristics of domain scores will be extracted, it is recognised that there will be lower levels of agreement. Similarly, associations to other outcome measures will be evaluated with ICCs, with a priori expectations of relative convergence amongst measures tapping overlapping concepts and experiences.

The measure will be considered a valid primary outcome for gender incongruence if inter-rate and test-retest reliability are both 0.7.

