4.4.2.6 Revised Child Anxiety and Depression Scale (RCADS)

The RCADS-25 ²⁰ is a 25-item measure used to assess symptoms of anxiety and depression in CYP. Each item is rated using a 4-point Likert scale (0= never; 3=always), with total scores ranging 0-45 on the anxiety subscale and 0-30 on the depression subscale. CYP self-report (RCADS-C-25) and parent-report (RCADS-P-25) versions will be administered. The parent-report measure has been adapted to include gender neutral language. Duration: 5 minutes.

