4.4.2.8 Utrecht Gender Dysphoria Scale – Gender Spectrum (UGDS-GS)

The UGDS-GS ²² is an 18-item questionnaire that measures gender dysphoria i.e. distress relating from the incongruence between an individual's birth registered sex and their gender identity, and gender affirmation i.e. comfort from living in accordance with their gender identity. Respondents are asked to rate each item using a 5-point Likert scale (1= disagree completely; 5= agree completely). Total scores range from 0-90, with higher scores indicating higher gender related distress. Only CYP self-report versions will be obtained. Duration: 3 minutes.

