Following the review, response categories/domains and anchor points will be selected in consultation focus groups with our young adult and parent Advisory Boards, gender care health professionals and CYP without gender incongruence drawn from the general population. Two parallel versions (CYP and parent) will be evaluated by these groups for face and content validity of the items, clarity of probes, appropriateness of anchor points and also to establish any domains/items not highlighted in the literature.

Field Testing

Field testing of the pilot interview will be undertaken among: CYP attending the CYPGS but not considered eligible for the PATHWAYS Trial; CYP not seeking GnRHa through puberty and are no longer eligible for puberty suppression; CYP who have already received GnRHa. We will recruit 75 CYP-parent dyads to complete two independent interviews, no more than one month apart. These interviews will be offered online or in person and will be audio-recorded and re-rated by a second researcher. The interview topic guide will include questions related to the core domains assessed in the KIDSCREEN-52, as well as other domains identified in the literature and by the young adult and parent Advisory Boards.

On the first interview occasion, participants will also be asked to complete key study questionnaire outcome measures (KIDSCREEN, RCADS, BIS-GS, UGDS-GS, CBC-L/YSR). This will provide

a psychometric dataset for test-retest and inter-rater reliability, CYP-parent agreement and convergent and discriminant validity.

Finally, using an online questionnaire of all domains, CYP and parents/carers/legal guardians will be asked to order a complete list of the domains to represent their personal priorities. For younger CYP and CYP/parents/carers/legal guardians with learning difficulties, the task can be supported by a researcher. This task will be completed on the first interview occasion alongside the key study questionnaire outcomes measures.

A purposive sample of 70 CYP-parent dyads will be invited to participate in a third interview 6-months after their baseline interview, in order to test the novel outcome measure's sensitivity to change.

Initial interviews and questionnaire completion will take 90-120 minutes and re-test interviews 60 minutes. Participants will be reimbursed £30 and £20 respectively for each session.

Please refer to Annex 2 (table 5) for the novel outcome measure schedule of events.

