1=protocol adherence; 2= personal priorities and quality of life; 3= gender; 4=mental health; 5= neurodevelopmental difference; 6=physical health; 7=adverse events **Information source:**

R=researcher-completed; SQ=self-reported questionnaire; PQ=parent-reported questionnaire; PQ**= parent reported questionnaire at baseline only; D=direct observation/examination

^{*} If a participant turns 16 during the study, consent must be sought

Table 4: Schedule of Events for information collected by clinicians/researchers

Event/Form	Domain, information source (see legend)	Baseline	Month 12	Month 24	Annual Follow Up	Ongoing*	Estimated completion time (minutes)
Registration form & consent	R (1)	X					5
Eligibility	R (1)	X					10
Medical history	D (6)	X					150
Demographic data	D (1)	X					2
Status form	R (1)		X	X	X		1
Withdrawal form	R (1)					X	2

LEGEND

Domains:

1=protocol adherence; 2= personal priorities and quality of life; 3= gender; 4=mental health; 5= neurodevelopmental difference; 6=physical health; 7=adverse events **Information source:**

R=researcher-completed; SQ=self-reported questionnaire; PQ=parent-reported questionnaire; D=direct observation/examination;

^{*} If a participant turns 16 during the study, consent must be sought

Table 5: Schedule of Events for novel outcome measure

Event/Form	Domain, information source (see legend)	Baseline	Follow-up (within 1-month of baseline)	Follow-up (within 6-months of baseline)	Estimated completion time	
					(minutes)	
Informed consent/ assent	SQ, PQ	X			10	
Interview	D (2) (3) (4) (6)	X	X	X	60	
Personal treatment priorities	SQ, PQ (2)	X			5	
Quality of Life (KIDSCREEN-52)	SQ, PQ (2)	X			7	
Anxiety and depression symptoms (RCADS-25)	SQ, PQ (4) (7)	X			5	
Gender dysphoria (UGDS-GS)	SQ (3)	X			3	
Body image/ dysphoria (BIS-GS)	SQ (3)	X			3	
Emotional & Behavioural Problems (CBCL, YSR)	SQ, PQ (4)	X			15	

Legend

Domains:

1=protocol adherence; 2= personal priorities and quality of life; 3= gender; 4=mental health; 5= neurodevelopmental difference; 6=physical health; 7=adverse events

Information source:

R=researcher-completed; SQ=self-reported questionnaire; PQ=parent-reported questionnaire; D=direct observation/examination

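### Section 8.7 measures association between differently scaled instruments with ICCs, and its rule for calling the novel measure valid rests on reliability alone

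*Protocol*

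**What the plan says.** Protocol section 8.7 names inter-rater and test-retest reliability as the most important properties of the new interview measure, both assessed by ICC on the total score. On validity it adds that "we also want to understand its convergent validity with the primary outcome measure, KIDSCREEN-10" and with other measures of mental health, behaviour, gender identity and body dysphoria. The statistic for this is also fixed: "associations to other outcome measures will be evaluated with ICCs", "with a priori expectations of relative convergence amongst measures tapping overlapping concepts and experiences".

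The decision rule follows: "The measure will be considered a valid primary outcome for gender incongruence if inter-rate and test-retest reliability are both 0.7".

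The comparators are described in section 4.4.2. For RCADS-25 the protocol gives scores "with total scores ranging 0-45 on the anxiety subscale and 0-30 on the depression subscale". For UGDS-GS it says "Total scores range from 0-90, with higher scores indicating higher gender related distress". Higher BIS-GS scores mean more dissatisfaction with the body, whereas higher KIDSCREEN scores mean better quality of life. The new total score has no metric yet.

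Section 4.8 plans a review of face and content validity, 75 dyads interviewed twice, and comparator questionnaires at the first interview for convergent and discriminant validity. On sensitivity to change it says: "A purposive sample of 70 CYP-parent dyads will be invited to participate in a third interview 6-months after their baseline interview". In Annex 2, Table 5, the corresponding column is headed "Follow-up (within 6-months of baseline", and only the interview itself is marked in it.

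**The concern.** An ICC asks how closely two sets of scores agree on one metric. That suits two raters, or two occasions, of the same interview. Between instruments with different units it mixes strength of association with differences in spread and, in the absolute-agreement form, in mean. Scales that run in opposite directions give a negative value. Section 8.7 intends to judge convergence by comparing instruments with one another, so differences in units could alter the very ordering it wants to read.

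The rule has a separate problem. Reliability is necessary for validity but does not establish it. A measure can be scored consistently by two raters, and be stable over a month, while measuring something other than its target. Following the rule as worded, the team would call such a measure a valid primary outcome whatever the convergent, discriminant or responsiveness results showed.

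**Working it through.** The protocol gives no derivation of the 0.7 threshold or of the 75 dyads, so there is no planned figure to reproduce. It gives no means or SDs for the comparators either; those below are assumptions.

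**1. ICC between instruments on different scales.** Let r be the Pearson correlation, s1 and s2 the SDs, and d the difference in means.

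- Consistency ICC = 2·r·s1·s2 / (s1² + s2²)
- Absolute-agreement ICC = 2·r·s1·s2 / (s1² + s2² + d²)

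Section 8.7 does not say which form is meant, so both are shown. Assume r = 0.8 throughout and a novel total with SD 15.

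| Comparator SD | d | Consistency | Absolute agreement |
|---|---|---|---|
| 7 | 22 | 168/274 = 0.61 | 168/758 = 0.22 |
| 6 | 40 | 144/261 = 0.55 | 144/1861 = 0.08 |
| 12 | 15 | 288/369 = 0.78 | 288/594 = 0.48 |

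All three comparators are equally related to the new measure, yet their ICCs differ in both forms. The order can also reverse. With equal SDs, r = 0.7 gives a consistency ICC of 0.70; with an SD ratio of 3, r = 0.9 gives 2·0.9·3/(1 + 9) = 0.54. With r = 0.7, SD ratios of 1, 1.5, 2, 3 and 5 give 0.70, 0.65, 0.56, 0.42 and 0.27. Reversing one scale changes only the sign. Pearson's r is unaffected by units, and reversing a scale changes only its sign. If scores are z-standardised and aligned in direction, s1 = s2 and d = 0, and the ICC formula reduces to r.

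**2. The decision rule.** Its only inputs are two reliability coefficients, so its outcome cannot depend on validity. A simulation confirms this (4,000 runs, 75 pairs, true reliability assumed 0.85, pass if both ICCs are at least 0.70). The pass rate was between 99.8% and 100% when the true correlation with the target construct was 0, 0.3, 0.6 or 0.9.

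**3. Precision of the threshold.** For an observed ICC of 0.70 from 75 pairs, F = (1 + 0.70)/(1 − 0.70) = 5.67. The 97.5% point of F on 74 and 74 degrees of freedom is about 1.58.

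- Lower: 5.67/1.58 = 3.58, giving (3.58 − 1)/(3.58 + 1) = 0.56.
- Upper: 5.67 × 1.58 = 8.97, giving (8.97 − 1)/(8.97 + 1) = 0.80.

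The chance that one coefficient reaches 0.70 is 0.215, 0.500 and 0.817 at true values of 0.65, 0.70 and 0.75. The chance that both do lies between the square of that value (independent estimates) and the value itself (fully dependent): 5–21%, 25–50% and 67–82%. The two estimates come from the same dyads, so the independent end is probably too low.

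**4. The third interview.** Section 4.8 places it at six months after the first; the Table 5 heading reads as any time up to six months. Table 5 marks every comparator questionnaire at baseline only.

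**The case against.** The size of the ICC distortion rests on assumed SDs and means, and most of the fall to 0.08–0.48 comes from the assumed mean differences. This stands: the consistency figures are the milder reading, and neither set is a prediction.

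The ICC form, standardisation and reverse-scoring could be set in the SAP, to which section 8.4 refers for further methods. A reader might infer that strong convergence will be reported as absent or negative. The protocol does not support that. Aligned z-scores would bring the ICC close to r, and a competent reader would not be misled by a negative value between scales known to run in opposite directions. What remains is that section 8.7 names the less suitable statistic without the condition that would make it work.

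A reader might also infer that validity goes unexamined. It does not: section 4.8 plans face, content, convergent and discriminant work and a sensitivity-to-change interview. The defect is that none of this enters the rule.

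Nor can it be said that change at the third interview will be uninterpretable. Section 3.3 seeks consent to use routine clinical outcomes and records, which might serve as an anchor, although no alignment with that interview is stated. Re-rating both interviews could also give more than 75 inter-rater pairs, in which case the interval of 0.56 to 0.80 would be somewhat too wide for that coefficient.

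Finally, the measure is not among the HORIZON outcomes in section 8.2 and enters no cohort model.

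**Conclusion.** Both central points hold as statements about section 8.7. The ICC is a poor measure of association between these instruments unless scores are standardised and aligned, which is not stated. Under the assumptions above, a true correlation of 0.8 would appear as about 0.55 to 0.78 in the consistency form and lower in the absolute-agreement form, and the ranking of comparators could change with their SDs alone. The rule for calling the measure valid contains no validity criterion; this needs no numerical assumption.

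The missing inequality sign, the absence of a confidence limit, the third-interview timing and the lack of a repeated comparator in Table 5 are secondary. This should be fixed, but it is confined to secondary objective 2. It would be going too far to infer that HORIZON's main results are at risk: the KIDSCREEN-10 primary analysis does not use the measure or the rule.

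**What to change.** In section 8.7:

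- Use Pearson or Spearman correlations with 95% confidence intervals for convergent and discriminant validity. State beforehand the expected sign for each comparator and the expected order of sizes. Keep ICCs for inter-rater and test-retest reliability.
- Reword the rule in two steps. The measure is *reliable* if both ICCs are at least 0.70, each reported with its 95% confidence interval. It is *valid* only if the pre-set convergent hypotheses also hold.

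Secondary changes: give the third interview one timing in section 4.8 and Table 5, and say what will serve as the anchor for change. Repeating a comparator there is one option. KIDSCREEN-52, which contains KIDSCREEN-10, is listed at 7 minutes per respondent, for up to 70 dyads.

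The changes to section 8.7 are wording only and need no extra data. They go through the amendment route in section 7.1, and should be made before field testing, since section 4.8 places this work in year 1. An added questionnaire would also be part of that amendment. The other cost is that the measure will be called valid less easily.
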